### Standard of Care

During the Extension Period, pharmacological antidepressant therapy can be modified only for non-responders or non-remitters. Those participants, who are classified as a responder or remitter at the End of the Core Period must maintain a stable SoC. In case of a relapse, the SoC pharmacological treatment can be adjusted, if needed, during the first 2 weeks of retreatment for relapse. Participants may or may not be hospitalized for the retreatment for relapse as per clinical judgment and local practices.

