### 3.3 Double-blind Extension Period

After completing the double-blind Core Period, all participants will enter the Extension Period for a minimum of 8 weeks and a maximum of 52 weeks.

Those participants who are not responders and not remitters at the end of the Core Period (see in this section, subsection Extension Follow-up duration for more details ), will be observed in an abbreviated Extension Period lasting 8 weeks only to obtain safety data and evaluate withdrawal and rebound effects of MIJ821. Because those participants did not respond to the treatment as defined in [Section 3.2](#) in the first instance, no retreatment will be provided in case of relapse. Those participants are allowed to adjust their SoC in their 8 weeks Extension Period, as necessary.

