#### **4.1.2 Rationale for choice of background therapy**

MIJ821 is intended as a short-term treatment to supplement SoC treatment in an emergency situation (patients with moderate to severe MDD who have suicidal ideation with intent). To ensure proper patient safety and to address the ethical concern of having patients on placebo with no treatment benefit, a pharmacological antidepressant background therapy as per local clinical practice and guidelines should be taken by all participants in the trial, on top of hospitalization (recommended period of 72 hours; with shorter or longer hospitalization duration allowed if clinically warranted per local standard practice, but not less than 24 hours) after the first study drug administration. To evaluate MIJ821 treatment in the appropriate context of SoC and because patients will be in an emergency situation, dosage titration or adjustments of standard-of-care antidepressant treatment will be allowed during the first 2 weeks of double-blind treatment, if needed, with dosages maintained thereafter during the Core Period. Psychotherapy is allowed.

In the Extension Period, pharmacological antidepressant therapy can be modified only for those participants who are not eligible for entering the 52 weeks Extension Period (see [Section 3.2](#) for more details) to allow therapy adjustments required to treat the MDD condition as per local clinical guidelines and practices.

By contrast, participants who at the End of the Core Period are eligible for entering the 52 weeks Extension Period (see [Section 3.2](#) for more details), will not be allowed to change their standard

of care treatment until a relapse since they have responded to the study treatment and need to continue the same therapy with the same regimen to allow evaluation of MIJ821 treatment response in the Extension Period.

[figure not shown]

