## **6.2 Other treatment(s)**

### **6.2.1 Concomitant therapy**

All participants must receive pharmacological antidepressant therapy during the Core Treatment Period and 52 weeks Extension Period. Pharmacological treatment may include an antidepressant, or antidepressant plus augmentation therapy (e.g. antipsychotics, lithium, etc). Dosage titration or adjustments of standard-of-care antidepressant treatment occurring during the first 2 weeks of double-blind treatment are allowed, if needed, with dosages maintained thereafter during the Core period.

Psychotherapy will also be allowed and any change must be appropriately documented in the source records and CRF.

Each concomitant drug must be individually assessed against all exclusion criteria/prohibited medication.

During the Extension Period, pharmacological antidepressant therapy can be modified only for non responders or participants who did not achieve remission (see [Section 3.2](#) for more details).

Those participants, who are classified as a responder or remitter at the End of the Core Period must maintain a stable SoC (see [Section 3.2](#) for more details). In case of a relapse, the SoC pharmacological treatment can be adjusted, if needed, during the first 2 weeks of retreatment. Participants may or may not be hospitalized for the treatment of relapse (as per clinical judgment and local practices).

Participants who are responder or remitter at the End of the Core Period, and relapse during the Extension Period but do not meet the weight requirements of 50-120kg (inclusive) to be retreated in case of relapse, may change their SoC, as required, and should discontinue the Extension as defined in [Section 3.3](#) Follow-up Duration.

All medications, procedures, and significant non-drug therapies (including physical therapy and blood transfusions) administered after the participant was enrolled into the study must be recorded on the appropriate Case Report Forms (CRFs).

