2.3.2 Prior, concomitant and post therapies

For the standardization of data display, concomitant medications and prior medications entered into the database will be coded using the World Health Organization (WHO) Drug Reference List, which employs the Anatomical Therapeutic Chemical classification (ATC) system. Non-drug therapies or procedures will be coded by Medical Dictionary for Regulatory Activities (MedDRA). The data analysis in this section will be based on the coded terminology. Frequency summary (count and proportion) will be provided by ATC (1, 3, 4) and coded name for medications, and by system organ class (SOC) and preferred term (PT) for non-drug therapies.

The missing or incomplete start/stop date of medication/therapy will be imputed before data handling (see imputation rule in [Appendix 5.1.2](#))

Standard of Care

[figure not shown]
Participants must receive pharmacological antidepressant therapy during study. Dosage titration or adjustments of SoC occurring within the first 2 weeks of Core Period are allowed, if needed, with dosages maintained thereafter during the Core period. The SoC includes antidepressant or augmentation, which will be identified by the category of “MDD Related Medications” from CRF form - “Concomitant medication” The SoC during Core Period will be summarized by ATC level (1, 3, 4) and preferred term.

The adjustment of SoC beyond the first 2 weeks potentially may lead to confounding effect to the efficacy assessments over 6 weeks in Core Period. So, any adjustment of SoC post the first 2 weeks will be flagged at individual participant level in listing and the impact on efficacy assessment will be indicated (e.g. adjustment of SoC beyond first 2 weeks in Core Period).

The adjustment of SoC will also not be allowed beyond the first 2 weeks of Retreatment Period. Any adjustments of SoC in Retreatment Period will be flagged similarly in listing but no summary will be provided.

Prohibited Medications and Therapies

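### Protocol Sections 3.3 and 6.2.1 give participants who respond but do not remit opposite instructions on changing antidepressants in the Extension, and the SAP neither flags such changes before relapse nor says how the relapse analysis treats them

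*Protocol*

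**What the plan says.** Protocol Section 3.3, under Standard of Care, sets two rules side by side. The permission reads "During the Extension Period, pharmacological antidepressant therapy can be modified only for non-responders or non-remitters". The obligation follows at once: "Those participants, who are classified as a responder or remitter at the End of the Core Period must maintain a stable SoC". Section 6.2.1 repeats the permission, saying that therapy "can be modified only for non responders or participants who did not achieve remission", and its next paragraph again requires responders and remitters to stay stable.

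Other places draw the line differently:

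- Section 3.2 (criteria to enter the 52-week Extension) admits Core completers who are responders **or** remitters at Day 43. It uses the non-responder / non-remitter label for those who fail to qualify.
- Section 3.3 (opening) speaks of participants who are neither responders nor remitters: "Those participants are allowed to adjust their SoC in their 8 weeks Extension Period, as necessary". The follow-up subsection of 3.3 uses the same neither/nor grouping.
- Section 4.1.2 says "pharmacological antidepressant therapy can be modified only for those participants who are not eligible for entering the 52 weeks Extension Period". It bars change until relapse for everyone eligible, so that treatment response can be evaluated in the Extension.

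On analysis, SAP 2.3.2 flags changes of standard of care (SoC) after week 2 of the Core Period, and for retreatment it says "Any adjustments of SoC in Retreatment Period will be flagged similarly in listing but no summary will be provided". It gives no flag for the time between Day 43 and relapse. SAP 2.5.2 plans relapse proportions up to 12 months and a Kaplan-Meier analysis of time to first relapse in responders/remitters. Its visible text has no rule for a SoC change before relapse.

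**The concern.** The permission joins two negatives with *or*, and the obligation joins the two positives with *or*. These are not complements: anyone who is a responder but not a remitter satisfies both. The protocol recognises this subgroup, because Section 3.4 gives it an extra relapse condition.

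Section 3.4 lists a need for SoC adjustment among the signs of clinical worsening, but a SoC change is not itself a relapse criterion. A change made early could therefore avert a confirmed relapse and be counted as relapse-free time. If sites read the rule differently, part of what the relapse curves show could be the changed background therapy. SAP 2.1 names time to relapse as a focus of the unblinded interim, whose purpose under SAP 1.1 is selection of the Phase 3 dose.

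**Working it through.** The plan states no figure on this point, so there is none to reproduce. The check has three parts.

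**1. Does the doubly instructed subgroup exist?** Inputs: baseline MADRS above 28, so at least 29 (Section 5.1); response is a fall of at least 50%, remission is a score of 12 or less (Section 3.2).

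- Smallest fall for a remitter: (29 − 12)/29 = 58.6%. Every remitter is therefore a responder, and the permission, read literally, covers all non-remitters.
- Overlap: Day 43 scores from 13 to half of baseline. That is 13–14 at baseline 29, 13–17 at 35 and 13–20 at 40. The overlap is non-empty at every eligible baseline.

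**2. How large could it be?** The documents give no Day 43 distribution, so this rests on assumption: scores normal, truncated at 0, mean 13 to 19, SD 9 to 11.

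Share of responders not in remission = [P(score ≤ B/2) − P(score ≤ 12)] / P(score ≤ B/2), with B/2 rounded down.

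Example, B = 35, mean 16, SD 9: P(≤ 17) = 0.526 and P(≤ 12) = 0.302, so the share is (0.526 − 0.302)/0.526 = 43%.

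| Baseline | Share of responders, over means 13–19 and SDs 9–11 |
|---|---|
| 29 | 16–26% |
| 32 | 28–43% |
| 35 | 32–49% |
| 40 | 42–62% |

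The ranges cover the calculation with and without a half-point continuity correction.

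**3. What could it do to the relapse proportion?** This is an illustration only. Let p be the relapse risk on stable SoC, s the share of responders not in remission, c the share of those who change SoC before relapse, and RR the relative risk after a change. Observed proportion = p × [1 − s × c × (1 − RR)]. Assume p = 30–50%, s = 20–50%, c = 10–50%, RR = 0.5.

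- Smallest shift within an arm: 0.30 × 0.20 × 0.10 × 0.5 = 0.3 points downward.
- Largest shift: 0.50 × 0.50 × 0.50 × 0.5 = 6.25 points downward.
- Spurious difference between arms with equal true risk, s = 20% on active and 50% on placebo: p × (0.50 − 0.20) × c × 0.5. This is 0.45 points at p = 30%, c = 10%, and 3.75 points at p = 50%, c = 50%.
- Standard error of a difference, with an assumed n = 10–20 responders per arm, √[2p(1 − p)/n]: 14.5 points (p = 30%, n = 20) to 22.4 points (p = 50%, n = 10).

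**The case against.** The best reply is that the intent is recoverable. Section 3.2 gives the non-responder / non-remitter label to participants who fail both criteria, and Section 3.3 may only be reusing it. The sentence beside the permission is mandatory, Section 4.1.2 is explicit, and Section 3.4 treats responders who are not in remission as part of the relapse population. On this view the fault is loose drafting in two sentences. That stands as to intent, but it does not remove the literal conflict. Section 6.2.1, the concomitant-therapy section, describes the permitted group as participants who did not achieve remission, which is not the Section 3.2 label.

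Tracking is also not wholly absent. Section 12.3 requires SoC adjustments during the study to be collected and summarized, Section 6.2.1 requires all medications to be recorded, and a breach might appear among the protocol deviations. So the data should exist. The SAP still summarizes SoC only for Core, while its Section 4 reports no change from the protocol's analyses. Some text in SAP 2.5 and 2.5.2 is redacted, so the absence of a handling rule can be asserted only for the visible text.

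A reader might also infer that weaker arms, placebo included, would leave more partial responders. As a count this fails under the model above: at baseline 35 and SD 9, the 13–17 band holds about 23% of an arm at mean 13 and 20% at mean 19. Only the share among responders rises, from about 36% to 49%.

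**Conclusion.** The contradiction within Sections 3.3 and 6.2.1 is real, and it applies to exactly the participants who respond with a Day 43 score above 12. The SAP's visible text neither flags nor handles SoC changes between Day 43 and relapse.

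A reader might go further and conclude that the relapse endpoint already mixes drug durability with changed therapy. The documents do not support that: it would require sites to act on the permission despite the adjacent obligation, and nothing shows that they did or would. Nor can one say that a third to a half of the relapse population is affected. The 16–62% range rests entirely on assumed distributions, and being in the subgroup does not mean that therapy was changed. In the illustration, distortion between arms is well below sampling error.

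The endpoint is secondary, with no estimand (SAP 2.5) and no hypothesis test (SAP 2.5.2). The primary 24-hour endpoint, alpha and power are untouched. The point is worth correcting because stable SoC is the protocol's own condition for interpreting the Extension, and time to relapse is examined at the interim.

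**What to change.** 1. **Protocol.** Reconcile the permission in Section 3.3 (Standard of Care) and Section 6.2.1 with Section 3.2, the rest of 3.3 and Section 4.1.2, so that one consistently worded instruction covers participants who respond but do not remit. Which rule applies is for the sponsor to decide.
2. **SAP 2.3.2.** Extend the SoC-adjustment flag to the time from Day 43 to relapse, in line with Protocol Section 12.3.
3. **SAP 2.5.2.** State how a SoC change before relapse is handled in the relapse proportions and the Kaplan-Meier analysis. Add one sensitivity analysis that counts the change as an event and one that censors at it, noting that censoring may be informative when worsening prompted the change.

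The cost is a wording correction in two protocol sections, one extra flag and two extra descriptive Kaplan-Meier runs on concomitant-medication data that the protocol already requires.

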### SoC can be adjusted or modified after the relapse retreatment, as clinically warranted. Extension Follow-up Duration

[figure not shown]
All participants must complete a follow-up period after the End of Core Period visit (Day 43):

- For participants who are neither remitters nor responders at the End of Core Period (Day 43) [Section 3.2](#), the follow up will last 8 weeks and consists of 3 mandatory visits (the 2 weeks Follow-up visit, the 4 weeks Follow up visit and the End of Study visit occurring 8 weeks after Day 43)
- For participants who are responders or remitters at the End of the Core Period (Day 43), and who do not experience any relapse, the Extension Period will last 52 weeks. This will consist of the 2 weeks Follow-up visit, the 4 weeks Follow-up visit, and thereafter Follow-up visits occurring every 4 weeks up to End of Study visit at Week 52
- Participants who are responders or remitters at the End of the Core Period (Day 43), and who relapse during the Extension Period, will receive one course of retreatment with MIJ821.
  - After that course of retreatment:
    - The participant will resume the 4 weekly Follow-up visit schedule (E.g., if the 6 weeks relapse retreatment period occurred from week 19 to 25, the participant will not perform visits week 20 and week 24, and will resume the follow-up at week 28).

- The duration of the follow up will be as per the initial schedule up to Week 52 or clinical worsening, whichever comes first, but they must complete at least 8 weeks follow-up period (see [Section 6.1.4](#)). Signs of clinical worsening may include worsening of depressive mood, need for SoC adjustments, a suicidal attempt, hospitalization for depression or suicidal ideation or behavior. For patient management see [Section 3.4](#), subsection Relapse and Clinical Worsening.
- Participants who are responders or remitters at the End of the Core Period (Day 43), and who relapse during the Extension Period but do not meet the weight requirements of 50-120kg (inclusive), cannot be retreated for the relapse and must be discontinued. The Extension period for these participants should last at least 8 weeks before the discontinuation.

The total duration of the Extension Period is 52 weeks, maximum. Therefore, the last date of confirmed relapse enabling access to the retreatment period is 38 weeks. If a participant relapses on or after that date, the participant must complete the End of Study visit as soon as possible.

**Figure 3-2 Study design in the extension in case of a relapse**

### 3.4 Criteria for retreatment in case of relapse

#### Relapse and clinical worsening

A relapse manifests as the appearance of new depressive symptoms or worsening of previously stable or improving MDD symptoms. During the Extension Period, participants experiencing deterioration must be assessed by the treating physician and the relapse must be confirmed by assessment with MADRS during scheduled or unscheduled visit.

Signs of clinical worsening may include worsening of depressive mood, need for SoC adjustments, a suicidal attempt, hospitalization for depression or suicidal ideation or behavior.

## Criteria for retreatment in case of relapse in the extension period

Meeting any of the following criteria will be considered a relapse and will be followed by a retreatment:

- MADRS total score  $\geq 22$  for 2 consecutive visits separated by 5-14 days AND meeting DSM-5 criteria for MDE (confirmed with M.I.N.I. Module A (Major Depressive Episode) to be eligible for relapse retreatment. The date of the first MADRS assessment will be the date of relapse. In addition, those participants who are responders at the End of Core period ( $\geq 50\%$  improvement) but are not remitters (MADRS  $\leq 12$ ), should demonstrate  $\geq 50\%$  worsening from their MADRS total score reported at the End of Core Period (End of Core Visit).

OR

- Hospitalization for worsening depression or any other clinically relevant event suggestive of a relapse (i.e. suicide attempt, or hospitalization for suicide prevention) AND meet DSM-5 criteria for MDE (independently of the MADRS score; confirmed by M.I.N.I. Module A (Major Depressive Episode). The start date of hospitalization will be the start date of relapse. In case of a clinically relevant event, without hospitalization, the start date of the event will be used as the relapse date.

Because assessments for relapse need to occur at two consecutive visits separated by 5-14 days, scheduled visits and/or unscheduled visits can be organized. Relapse confirmation can be performed either at the Pre-retreatment visit or before the first infusion given for retreatment. If several relapse criteria are met, the first will be defined as the date of relapse.

In case of clinical worsening after participant already received one course of retreatment for relapse, the patient must be discontinued, as soon as 8 week follow up from the last dose of MIJ821 was administered. These patients will be managed according to investigator judgement with SoC that can be adjusted or modified after the relapse retreatment, as clinically warranted.

## 4 Rationale

### 4.1 Rationale for study design

The study design, patient population, background treatment (pharmacologic standard of care), endpoints, inclusion and exclusion criteria are aligned with regulatory guidelines such as the draft guidance for developing drugs for treatment major depressive disorder ([FDA 2018](#)) and EMA guideline for Clinical investigation of medicinal products in the treatment of depression ([EMA 2013](#)). This protocol was developed in consultation with EMA and FDA.

The choice of treatment duration and timing of assessment of primary and other endpoints is based on the MIJ821 rapid mechanism of action, as well as the expected onset and durability of the treatment effect as demonstrated in the proof of concept study in patients with treatment-resistant depression (CMIJ821X2201). The treatment resistant depression (TRD) population represents a subtype of the overall MDD population and, therefore, the safety and efficacy data obtained from the PoC study in TRD patients are generalizable to the overall MDD population including the targeted population of MDD patients with suicidal ideation with intent.

To ensure patient safety and to comply with clinical practice, the double-blind Core Period will be conducted first in an inpatient setting and later in an outpatient treatment setting, as appropriate. The Core Period includes a weekly visit schedule for efficacy assessment and safety monitoring.

To allow evaluation of durability of the initial response and the potential effect of MIJ821 on relapses long term, as well as to evaluate MIJ821 safety after a repeated use, a 12-month extension follows the 6 weeks Core Period.

#### **4.1.1 Rationale for primary efficacy endpoint**

According to FDA draft guidance for developing drugs for the treatment of major depressive disorder ([FDA 2018](#)) when compared to 6-8 weeks for antidepressants of established classes, for rapid-acting novel antidepressants, an earlier primary efficacy endpoint would be appropriate.

In the PoC study (CMIJ821X2201), MIJ821 demonstrated a compelling treatment effect compared to placebo for both doses tested at 24 hours post dose. Based on these data a 24 hour time point was chosen to assess the primary variable.

Based on the rapid mode of action of MIJ821, the primary efficacy endpoint of this study is to assess the treatment effect of an extended dose range for MIJ821 (4 doses) vs placebo at 24 hours after the first intravenous infusion of investigational drug.

The efficacy will be determined by using the MADRS ([Montgomery and Asberg 1979](#)) which is a gold standard scale for the evaluation of major depressive episodes and widely used for registration studies in depression.

#### **4.1.2 Rationale for choice of background therapy**

MIJ821 is intended as a short-term treatment to supplement SoC treatment in an emergency situation (patients with moderate to severe MDD who have suicidal ideation with intent). To ensure proper patient safety and to address the ethical concern of having patients on placebo with no treatment benefit, a pharmacological antidepressant background therapy as per local clinical practice and guidelines should be taken by all participants in the trial, on top of hospitalization (recommended period of 72 hours; with shorter or longer hospitalization duration allowed if clinically warranted per local standard practice, but not less than 24 hours) after the first study drug administration. To evaluate MIJ821 treatment in the appropriate context of SoC and because patients will be in an emergency situation, dosage titration or adjustments of standard-of-care antidepressant treatment will be allowed during the first 2 weeks of double-blind treatment, if needed, with dosages maintained thereafter during the Core Period. Psychotherapy is allowed.

In the Extension Period, pharmacological antidepressant therapy can be modified only for those participants who are not eligible for entering the 52 weeks Extension Period (see [Section 3.2](#) for more details) to allow therapy adjustments required to treat the MDD condition as per local clinical guidelines and practices.

By contrast, participants who at the End of the Core Period are eligible for entering the 52 weeks Extension Period (see [Section 3.2](#) for more details), will not be allowed to change their standard

of care treatment until a relapse since they have responded to the study treatment and need to continue the same therapy with the same regimen to allow evaluation of MIJ821 treatment response in the Extension Period.

[figure not shown]
